### 6.11.3 Key Secondary Endpoints

All the secondary efficacy analyses will be performed on the ITT population. The following key secondary endpoints will be analyzed. For all time to event analysis, estimates and 95% confidence

intervals of the 25th, 50th and 75th quantiles will be reported. The hazard ratio, 95% confidence interval, and p-value of voclosporin versus placebo will be reported. A Kaplan-Meier plot with both treatment arms will also be provided.

#### 6.11.3.1 Time (weeks) to UPCR of $\leq 0.5$ mg/mg

Time to UPCR of  $\leq 0.5$  mg/mg will be analyzed by comparing the survivor function between treatment arms. It will be estimated using Kaplan-Meier methodology and will be presented as a plot showing a line for each treatment group as well as the numbers remaining at risk for each treatment group at different time points. Median time to UPCR of  $\leq 0.5$  mg/mg along with two-sided confidence intervals will be displayed. Time to event will be measured as the number of weeks from day of randomization to the day of the event. Subjects who do not experience an event will be censored on the day of their last assessment of UPCR.

A Cox's proportional hazards model will be fitted to assess the significance of the differences between treatment arms. The model will include terms for treatment arm, baseline UPCR, biopsy class, MMF use at baseline and region. Estimates of the treatment effects will be expressed as hazard ratios (and associated 95% CI) for voclosporin relative to placebo. Hazard ratios greater than unity will indicate the hazard to be greater for voclosporin than for placebo and therefore indicate that the events in question generally occur earlier on active voclosporin and, for this endpoint, a benefit of voclosporin (Table 14.2.2). The log-log survivor function to proportional hazards will be assessed. A listing of time (weeks) to UPCR of  $\leq 0.5$  mg/mg responders and censors will be provided.

#### 6.11.3.2 Partial renal response as defined by 50% reduction from baseline UPCR at Weeks 24 and 52

Change from baseline in UPCR will be calculated as the post baseline measurement minus the baseline measurement. Percent change from baseline will be calculated as:

- Percent change from baseline (UPCRpc) =  $\left( \frac{\text{Change from baseline}}{\text{Baseline}} \right) \times 100$

A 50% reduction in UPCR will be indicated by UPCRpc  $\leq -50$ . Subjects with missing UPCRpc values will be considered non-responders. This endpoint will be analyzed and presented similarly to the primary efficacy endpoint as described in Section 6.11.2 (Table 14.2.3). A listing of subjects considered responders will be provided.

A supplementary analysis of partial response at both Week 24 and Week 52 will be undertaken using the alternative baseline definition (Section 6.2.2) of the lowest UPCR value pre-dosing.

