Procedures:	
See Schedule of Events for full details of protocol required procedures and applicable visits (and timings). Subjects who have provided signed and dated informed consent will be screened for entry into this study. Baseline proteinuria level is determined by a mean of 2 first morning void urine samples taken during the screening period. If a subject has not had a kidney biopsy within the required timeframe for study eligibility, one may be performed to assess eligibility into the study, provided consent is in place and provided the results are received before randomization. Subjects meeting the required eligibility criteria will be randomized in a ratio of 1:1 to receive either Orelvo (23.7 mg BID) or matching placebo starting on Day 1. All subjects will receive initial treatment with 0.5 to 1.0 g IV methylprednisolone. In consultation with the Medical Monitor, and if it is in the subject's best interest, IV methylprednisolone may be started during the screening period. Subjects receiving IV methylprednisolone in the 3 months prior to screening must be discussed with the Medical Monitor prior to initiating further IV methylprednisolone. For subjects who are not already taking prescribed MMF prior to randomization, the dosing of MMF will start at 500 mg BID for a total daily dose of 1 g/day for the first week, increasing to 1 g BID for a total daily dose of 2 g/day for the second and subsequent weeks (i.e., beginning on Day 8).
 
All subjects will complete dosing through 52 weeks of study treatment. Subjects who permanently discontinue study treatment before the Week 52 visit will return for all remaining study visits and assessments unless they have withdrawn consent. All subjects who complete participation and study treatment through 52 weeks and provide consent will have the opportunity to enroll into a continuation study for which the details are not yet finalized.

Sample Size:	
A 2 group continuity corrected Chi square test with a 0.05 two-sided significance level will have 80% power to detect the difference between a placebo response rate of 20.0% and an Orelvo response rate of 34.4% (odds ratio=2.1) when the sample size in each group is 162 (total N=324). While the effect of withdrawals will be investigated, subjects withdrawing for any reason will be counted as non-responders in the primary analysis and therefore no adjustment of sample size for withdrawals is necessary.

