### **5.6.1 Discontinuation from Study Treatment Due to Early Non-response to Therapy**

Subjects will be discontinued from study treatment if their early disease response is suboptimal. The Investigator must contact the Medical Monitor to discuss further continuation in the study if the subject meets 1 of the 2 following criteria:

- After 12 weeks of treatment, the subject shows a >30% decrease from baseline value in CKD-EPI eGFR in 2 successive measurements separated by at least 4 weeks

or

- After 8 weeks of treatment, the subject shows a confirmed reduction in UPCR of  $\leq 25\%$  assessed by 2 consecutive measurements at least 2 weeks apart.

If the subjects require treatment with IV methylprednisolone or any rescue medication other than that permitted in the protocol (see Section 7.2.2.2, [Corticosteroids](#)), they should be permanently discontinued from the study treatment and will be considered a treatment failure. Subjects who are permanently discontinued from study treatment will be treated as deemed appropriate by the Investigator.

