## 4 SAMPLE SIZE

The total sample size will be approximately 324 subjects (162 subjects per treatment arm). This is based on the following assumptions:

- A two group continuity corrected Chi square test with a 0.05 two-sided significance level will have 80% power to detect the difference between a placebo response rate of 20.0% and a voclosporin response rate of 34.4% (odds ratio=2.1) when the sample size in each group is 162 (total N=324).
- The effect of withdrawals will be investigated. Subjects withdrawing for any reason will be counted as non-responders in the primary analysis and therefore no adjustment of sample size for withdrawals is necessary.
- The impact of withdrawals on primary endpoint will be investigated in the tipping point analysis.

Table 4.1 shows the voclosporin response rates required to maintain a minimum 80% power at the planned sample size for given placebo response rates. These response rates all lead to odds ratios of around 2, which is a clinically relevant effect.

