### **6.11.3.3 Time to 50% reduction in UPCR from baseline**

Time to 50% reduction in UPCR will be analyzed similarly to the end point described in Section 6.11.3.1. The definition and calculation of 50% reduction in UPCR is consistent with that described in Section 6.11.3.2 (Table 14.2.4). A listing of time (weeks) to a 50% reduction in UPCR, and censors will be provided.

A supplementary analysis of time to 50% reduction in UPCR will be undertaken using the alternative baseline definition (Section 6.2.2) of the lowest UPCR value pre-dosing.

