### **6.11.3.4 Renal response at Week 24**

- Renal response at Week 24 will be adjudicated by the CEC and also programmatically derived using similar definitions to those used to derive response at week 52. Steroid dosing will be assessed between weeks 16 and 24 and only rescue medication taken prior to the week 24 assessment will disqualify a subject from response.
- Renal response at week 24 (adjudicated and programmed) will be analyzed in a similar manner to that described in Section 6.11.2 (Table 14.2.5.1 and 14.2.5.2).

A listing of subjects with renal response at Week 24 will be provided.

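### Rescue disqualifies a subject only from renal response; the other four Hochberg-tested key secondary comparisons have no rescue rule and are not reconciled with the treatment-failure statement in protocol 5.6.1

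*SAP*

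**What the plan says.** SAP 6.11.5.2 lists five key secondary comparisons for the Hochberg procedure: time to UPCR ≤0.5 mg/mg, partial renal response at Week 52, partial renal response at Week 24, time to 50% UPCR reduction, and adjudicated renal response at Week 24.

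Only the last has a rescue rule. SAP 6.11.3.4 states that "only rescue medication taken prior to the week 24 assessment will disqualify a subject from response". For the primary endpoint, SAP 3.1 and 6.11.1 likewise make rescue a non-response.

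The other four are defined by UPCR alone:

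- **Partial response (SAP 6.11.3.2):** a fall of at least 50% from baseline. The only handling rule is "Subjects with missing UPCR pc values will be considered non-responders".
- **Time to UPCR ≤0.5 mg/mg (SAP 6.11.3.1):** subjects without an event are censored at their last UPCR assessment.
- **Time to 50% reduction (SAP 6.11.3.3):** analyzed in the same way. "The definition and calculation of 50% reduction in UPCR is consistent with that described in Section 6.11.3.2".
- **General rule (SAP 6.2.4):** for endpoints that do not include death, deaths are censored. Rescue is not mentioned.

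Protocol 5.6.1 says of subjects who need IV methylprednisolone or rescue that the protocol does not permit that "they should be permanently discontinued from the study treatment and will be considered a treatment failure". Their later treatment is left to the investigator. The protocol synopsis adds: "Subjects who permanently discontinue study treatment before the Week 52 visit will return for all remaining study visits and assessments", unless consent is withdrawn.

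**The concern.** UPCR continues to be measured after rescue, so the missing-data rule does not catch a rescued subject who remains in follow-up. If the investigator's later treatment lowers UPCR past a threshold, that subject becomes a responder or has an event credited to the randomized arm, although the protocol has already called the same subject a treatment failure. A subject rescued before Week 24 could be a non-responder for renal response and a responder for partial renal response at the same visit, within the same alpha-controlled family.

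The early non-response criteria in protocol 5.6.1 include a weak UPCR fall after 8 weeks. The subjects likeliest to move to other therapy may therefore be those doing poorly on the variable that is later scored. Four of the five key secondary comparisons could then mix the effect of study drug with the effect of rescue, in a proportion the plan neither states nor examines.

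**Working it through.** **1. Which comparisons have a rescue rule?**

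| Comparison | Rescue rule | Other stated handling |
|---|---|---|
| Primary: renal response, Week 52 | Yes (SAP 3.1, 6.11.1) | Insufficient data = non-response |
| Renal response, Week 24 | Yes (SAP 6.11.3.4) | As for Week 52 |
| Partial response, Week 24 | None | Missing UPCR = non-response |
| Partial response, Week 52 | None | Missing UPCR = non-response |
| Time to UPCR ≤0.5 | None | Censored at last UPCR; deaths censored |
| Time to 50% reduction | None | As above |

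So four of the five key secondary comparisons have none. For Week 24 partial response only rescue before Week 24 matters. For the time-to-event endpoints only a threshold *first* reached after rescue matters.

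**2. Reproduce the plan's own power.** SAP section 4: "A two group continuity corrected Chi square test with a 0.05 two-sided significance level will have 80% power" for 20.0% v 34.4% "when the sample size in each group is 162 (total N=324"). With p̄ the mean of the two rates and n per arm,

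z = [ |p₁ − p₂| − 1/n − 1.96·√(2p̄(1 − p̄)/n) ] / √[(p₁(1 − p₁) + p₂(1 − p₂))/n], power = Φ(z).

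z = (0.1440 − 0.0062 − 1.96 × 0.0494) / 0.0488 = 0.84, so power is 79.9%. Solving for n gives 163 per arm against the stated 162. The plan's figure reproduces.

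**3. Illustrate the gap for partial response.** The documents give no rescue rate, no response rate after rescue and no partial-response rate, so all of these are assumptions:

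- 50% (placebo) v 65% (active) when rescue counts as failure;
- half of rescued subjects later meet the UPCR threshold.

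Points added to an arm by UPCR-only scoring = rescue rate × 0.5. The same power formula is used with n = 162.

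| Rescue, placebo / active | Points added | Scored rates | Difference | z | Power |
|---|---|---|---|---|---|
| Rescue counted as failure | – | 50.0% v 65.0% | 15.0 | 0.67 | 75% |
| 15% / 8% | 7.5 / 4.0 | 57.5% v 69.0% | 11.5 | 0.07 | 53% |
| 8% / 15% | 4.0 / 7.5 | 54.0% v 72.5% | 18.5 | 1.40 | 92% |
| 10% / 10% | 5.0 / 5.0 | 55.0% v 70.0% | 15.0 | 0.72 | 77% |

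Without the 1/n correction the first three powers are 78%, 57% and 94%; the pattern is the same.

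**4. Vary the response after rescue.** Now let 50% v 65% be the success rates in non-rescued subjects only, and let 30% to 70% of rescued subjects later meet the threshold. With rescue rate r, non-rescued success s and success after rescue q, the failure rule gives (1 − r)s and UPCR-only scoring gives (1 − r)s + rq.

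- **10% / 5% rescue:** the failure rule gives 0.90 × 0.50 = 45.0% v 0.95 × 0.65 = 61.75%, odds ratio 1.97. UPCR-only scoring gives 1.86 down to 1.73. About 5 to 11 placebo and 2 to 6 active subjects are reclassified (162 × r × q).
- **5% / 10% rescue:** 1.56 under the failure rule, 1.66 up to 1.82 under UPCR-only scoring.
- **5% / 5% rescue:** 1.78 against 1.79 to 1.80.

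The sign follows the imbalance in rescue, and with equal rescue the effect nearly vanishes.

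**The case against.** The case on the other side has real weight.

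- **A reader might infer that the SAP breaches the protocol.** The documents do not support that. Protocol 5.6.1 concerns stopping treatment and does not define treatment failure as an analysis status. The protocol's own endpoint lists (3.3.2.1 and 13.7.2.1) make partial response and the two time-to-event endpoints UPCR-only, and the SAP carries them over. This stands: the inconsistency is within the protocol as well as between the documents.
- **Scoring UPCR regardless of rescue is a legitimate treatment-policy strategy on an ITT population, and renal response already supplies the composite view.** This stands as a principle. But the SAP never states that strategy for these endpoints: the intercurrent-event list in SAP 3.1 is written for the primary estimand only.
- **SAP 6.11.3.2 refers to the primary analysis, which might seem to import the rescue criterion.** It points to 6.11.2, which covers the adjudication process and the logistic model. The rescue criterion is in 6.11.1, and 6.11.3.2 sets its own response rule.
- **A reader might infer that stopping study drug should itself mean failure.** It should not: SAP 3.1 assesses such subjects for response even on the primary endpoint. Rescue is the decisive event.
- **A reader might infer from the Week 8 criterion that as much as 44 weeks (52 − 8) of post-rescue UPCR counts.** That criterion prompts a discussion with the Medical Monitor after two measurements at least 2 weeks apart. It does not time rescue, so the figure does not follow.
- **The illustration uses a stand-alone chi-square at 0.05.** The planned test is a covariate-adjusted logistic regression within a Hochberg family, so the powers show scale only.

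**Conclusion.** The gap is real and worth closing. Rescue disqualifies a subject only from renal response. On the other four Hochberg-tested comparisons, a threshold first met after rescue counts in the subject's favour, while protocol 5.6.1 describes that subject as a treatment failure. The two statements need to be reconciled.

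A reader might infer that the plan is tilted towards voclosporin, or simply loses power. The documents support neither: with more rescue on placebo the present scoring is conservative, and with more on active it flatters the drug. The range from 53% to 92% around a 75% reference rests entirely on assumed rates.

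The primary endpoint and the sample size are unaffected, because the primary endpoint already scores rescue as non-response.

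**What to change.** Before unblinding, reconcile SAP 6.11.3.1 to 6.11.3.3 with protocol 5.6.1.

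- **Partial response at Weeks 24 and 52:** score a subject with CEC-adjudicated rescue before the visit as a non-responder at that visit, as 6.11.3.4 already does for Week 24 renal response.
- **The two time-to-event endpoints:** do not count a threshold first reached after rescue as an event. Keep the subject in the risk set rather than censoring at rescue. State how this sits with the censoring of deaths in 6.2.4, since otherwise rescue would be penalised and death would not.
- **Data:** record the date of first adjudicated rescue. The CEC already reviews medication listings and adjudicates rescue (6.11.1), and its decision already feeds the programmed Week 52 endpoint (6.11.2.3), but the SAP does not say that it assigns a date.
- **Supplementary analysis:** keep the version that ignores rescue.

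The cost is SAP wording, a small amount of programming and possibly one more adjudication field. Reported response rates fall in both arms, for example by 7.5 points on placebo and 4.0 on active under the 15% / 8% assumption.

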### **6.11.3.3 Time to 50% reduction in UPCR from baseline**

Time to 50% reduction in UPCR will be analyzed similarly to the end point described in Section 6.11.3.1. The definition and calculation of 50% reduction in UPCR is consistent with that described in Section 6.11.3.2 (Table 14.2.4). A listing of time (weeks) to a 50% reduction in UPCR, and censors will be provided.

A supplementary analysis of time to 50% reduction in UPCR will be undertaken using the alternative baseline definition (Section 6.2.2) of the lowest UPCR value pre-dosing.

### **6.11.3.4 Renal response at Week 24**

- Renal response at Week 24 will be adjudicated by the CEC and also programmatically derived using similar definitions to those used to derive response at week 52. Steroid dosing will be assessed between weeks 16 and 24 and only rescue medication taken prior to the week 24 assessment will disqualify a subject from response.
- Renal response at week 24 (adjudicated and programmed) will be analyzed in a similar manner to that described in Section 6.11.2 (Table 14.2.5.1 and 14.2.5.2).

A listing of subjects with renal response at Week 24 will be provided.

### **6.11.4 Other Secondary Endpoints**

The other Secondary endpoint analyses will be performed on the ITT population.

#### **Change from baseline endpoints**

Change from baseline in UPCR endpoints will be analyzed using a Mixed Effect Model Repeated Measures analysis with treatment arm, visit, treatment by visit interaction, biopsy class, MMF use at baseline, region and baseline UPCR included as a covariates in the model. Results will be expressed as differences between treatment arms (along with the associated 95% CI). The observed and change from baseline values will be summarized by treatment visit and treatment arms. The LS means and their corresponding 95% CI of the change from baseline values will also be presented for each visit and for the overall change. The model will be fitted using an unstructured (UN) covariance matrix. Should the UN covariance matrix not converge, then an autoregressive (AR(1)) covariance matrix will be used. The covariance matrix used will be indicated in the footnotes. The Kenward-Roger degree of freedom adjustment will be applied. LS mean plots of mean change from baseline versus visit will be presented for UPCR and eGFR.

The SAS code anticipated to be used for analysis of the change from baseline endpoints is as follows:

```
Proc Mixed data=dataset;  
Class Treatment biopsy_class MMF_use Region visit subject;  
Model response = Treatment biopsy_class MMF_use Region visit visit*treatment baseline/ DDFM=KR  
Repeated Visit/subject =subject Type= UN R Corr;  
LSmeans visit*treatment/PDIFF CL E;  
Run;
```

#### 6.11.4.1 Duration of UPCR $\leq 0.5$ mg/mg

Duration of UPCR  $\leq 0.5$  mg/mg refers to the time (weeks) from the onset of the first UPCR  $\leq 0.5$  mg/mg to the subsequent, second occurrence of UPCR  $>0.5$  mg/mg (i.e., allowing a single spike in UPCR). An event occurs at the time of the subsequent, second UPCR  $>0.5$  mg/mg. Subjects who do not experience a subsequent, second UPCR  $>0.5$  mg/mg will be censored at the date of the last UPCR assessment. Only subjects who achieved an initial response (UPCR  $\leq 0.5$  mg/mg) will be included in the analysis of this endpoint. Duration of UPCR  $\leq 0.5$  mg/mg will be analyzed in a similar manner to that described in Section 6.11.3.1 (Table 14.2.6).

An additional summary of this endpoint will be undertaken by summing the weeks between each UPCR measure  $\leq 0.5$  mg/mg and a subsequent measure  $>0.5$  mg/mg. This will give an approximation of time spent with UPCR  $\leq 0.5$  mg/mg for each subject. This will be summarized and analyzed as a continuous endpoint and comparison between both treatment arms will be carried out using a 2 sample Wilcoxon test.

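### Duration of UPCR ≤0.5 mg/mg is tested between arms by a Cox model only in subjects who responded after randomisation, so its hazard ratio and p-value are not a randomised comparison

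*SAP*

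**What the plan says.** SAP 6.11.4.1 defines duration of UPCR ≤0.5 mg/mg as a time to event. The time "refers to the time (weeks) from the onset of the first UPCR" value at or below 0.5, so the clock starts after randomisation. The event is the second later value above 0.5. A subject without that event "will be censored at the date of the last UPCR assessment". The analysis set is stated directly: "Only subjects who achieved an initial response" are included.

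The method is given by reference to SAP 6.11.3.1, which has Kaplan-Meier curves and this model: "A Cox's proportional hazards model will be fitted to assess the significance of the differences between treatment arms". Its covariates are baseline UPCR, biopsy class, MMF use and region. For time-to-event analyses SAP 6.11.3 adds the output: "The hazard ratio, 95% confidence interval, and p-value of voclosporin versus placebo will be reported". Protocol 13.8.3.2 likewise lists this duration among the endpoints analysed by Kaplan-Meier and Cox. Neither document labels the comparison descriptive.

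On population, SAP 6.11.4 says: "The other Secondary endpoint analyses will be performed on the ITT population". Protocol 13.8.3 says the same of all secondary efficacy analyses.

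A second paragraph of SAP 6.11.4.1 adds, for each subject, a sum of the weeks between a value at or below 0.5 and a later value above it, compared between arms by a two-sample Wilcoxon test. It has no rule for subjects who never reach 0.5 and none for a period still open at the last assessment.

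SAP Section 9 takes the endpoint out of the key secondary list, and it is absent from the Hochberg list in SAP 6.11.5.2.

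**The concern.** Randomisation makes the arms comparable at baseline. It does not make comparable two subgroups picked by an outcome that treatment is meant to change. The sample size rests on a higher Week 52 renal response on voclosporin, and time to UPCR ≤0.5 is a key secondary endpoint. The plan therefore expects the voclosporin responders to include people who would not have responded on placebo. If those added responders relapse faster or slower than the rest, the responder-only hazard ratio reflects that mix, whether or not the drug changes how long anyone's response lasts.

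At stake is the meaning of the one hazard ratio and p-value the plan attaches to duration of response. A reader would naturally take it as an effect on durability.

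**Working it through.** **1. The plan's own figure.** The documents give no sample size, power or event count for this endpoint. The primary-endpoint calculation (SAP Section 4) supplies the arm size and planning rates used below, so it is checked first. Inputs: 20.0% v 34.4%, two-sided 0.05, 80% power, continuity-corrected chi-square.

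- Mean rate 0.272; difference d = 0.144.
- Uncorrected n' = [1.960·√(2·0.272·0.728) + 0.842·√(0.2·0.8 + 0.344·0.656)]² / 0.144² = 148.7, i.e. 149.
- Corrected n = (n'/4)·[1 + √(1 + 4/(n'd))]² = 162.3 per arm (163 if rounded up).

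The stated 162 reproduces.

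**2. Who enters the responder-only model.** Assumption: reaching UPCR ≤0.5 at some time is as frequent as the planned Week 52 renal response. The documents give no rate for ever reaching it.

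- Placebo: 162 × 0.200 = 32.4.
- Voclosporin: 162 × 0.344 = 55.7.
- Total: about 88 of 324 randomised.

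**3. How far the groups differ in make-up.** Further assumption: everyone who would respond on placebo would also respond on voclosporin. The share of voclosporin responders who respond only on the drug is then 1 − (placebo rate / voclosporin rate).

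| Placebo / voclosporin rate | Share responding only on voclosporin |
|---|---|
| 15% / 28.4% (SAP Table 4.1) | 47% |
| 20% / 34.4% (SAP Section 4) | 42% |
| 25% / 40% (SAP Table 4.1) | 37.5% |
| 40% / 60% (assumed) | 33% |
| 45% / 65% (assumed) | 31% |

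**4. What this can do to the hazard ratio.** Simulation, 1,000 trials per row, 162 per arm, 20% v 34.4% responding. Treatment has no effect on any subject's duration. Relapse is exponential with a 40-week median in those who respond on either arm. Follow-up after response is uniform over 4 to 44 weeks. The Cox model is unadjusted. The first column is the relapse hazard of the drug-only responders relative to the others.

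| Relative relapse hazard (assumed) | Median HR | Nominal p<0.05 | Mean events |
|---|---|---|---|
| 0.5 | 0.76 | 9.5% | 26 |
| 1 | 1.02 | 3.4% | 29 |
| 1.5 | 1.21 | 4.4% | 31 |
| 2 | 1.36 | 10.7% | 34 |
| 3 | 1.69 | 26.8% | 37 |

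At 40% v 60%, relative hazards of 0.5 and 1 gave median HRs of 0.83 and 0.99.

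A second set of assumptions used 45% v 65% responding, onset uniform over Weeks 4 to 30, a base relapse hazard of 0.010 per week, censoring at Week 52 and 2,000 trials per setting. Relative hazards of 0.5, 1, 2 and 3 gave median HRs of 0.84, 0.99, 1.29 and 1.48, with nominal significance in 9%, 4%, 14% and 31%.

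**5. Reading the direction.** The event is loss of response, so a hazard ratio above 1 counts against voclosporin. Rows with a relative hazard above 1 therefore penalise the drug; the 0.5 row favours it. The hazard ratio centres on 1 only when the added responders relapse at the same rate as the others. The trial cannot verify that, because drug-only responders cannot be identified.

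**The case against.** **The endpoint carries no confirmatory weight.** This stands. It is outside the Hochberg family, and no alpha, sample size or primary result depends on it. A reader might infer that the trial's confirmatory conclusions are exposed; SAP 6.11.5.2 and Section 9 show that they are not.

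**Restricting to responders does not contradict the ITT statement.** Largely right. A reader might infer that SAP 6.11.4.1 contradicts SAP 6.11.4 and Protocol 13.8.3. The better reading is a general rule with an endpoint-specific restriction: a duration that starts at first response has no start in someone who never responds. The restriction is openly stated, but the exception is not declared where the general rule is given.

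**An all-subject comparison is already planned.** Partly right. The second paragraph of SAP 6.11.4.1 speaks of each subject and would fall under the ITT statement. But it follows the sentence limiting the endpoint's analysis to responders and states no zero for never-responders. Because it sums only up to a later value above 0.5, it also gives no time to a period still in response at the last assessment. It cannot serve as the randomised comparison as written.

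**The simulated rates are invented.** This stands as a limit on their use. The relapse ratios are assumptions, and the planning response rates belong to a different endpoint. The simulated model omits the SAP's covariates, the visit spacing and the second-occurrence event rule. Adjustment may absorb part of the difference in responder mix, but four baseline terms cannot be relied on to restore comparability. A reader might take 27% or 31% as the expected false-positive rate, or suppose that the bias flatters voclosporin. The documents support neither: those figures need a threefold relapse hazard, and in that setting the bias runs against the drug.

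**Conclusion.** The concern holds as a matter of design. SAP 6.11.4.1, with 6.11.3, 6.11.3.1 and Protocol 13.8.3.2, commits to a between-arm hazard ratio and p-value in a group selected by a post-randomisation outcome that treatment is expected to change. That is not a randomised comparison.

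The direction and size of any distortion cannot be known from the documents. With no durability effect, median hazard ratios from 0.76 to 1.69 arose when the relapse hazard of drug-only responders was assumed to be 0.5 to 3 times that of the others. At 1.5 times, nominal significance (4.4%) stayed close to 5%. These results show possibility; they do not estimate what this trial will see. The consequence is confined to any claim about duration of response.

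**What to change.** 1. In SAP 6.11.4.1, keep the Kaplan-Meier estimate among responders as a description by arm, and drop the between-arm Cox hazard ratio and p-value. Record this in SAP Section 9 as a change from Protocol 13.8.3.2.
2. Make the Wilcoxon test of the second paragraph the between-arm comparison, on all randomised subjects. The variable is total weeks with UPCR ≤0.5 through Week 52. Assign 0 weeks to subjects who never reach it. Count a period still at or below 0.5 at the last UPCR assessment up to that assessment, without requiring a later value above 0.5.
3. State that this variable measures time in response, combining whether, when and for how long subjects respond, and that it does not isolate durability. It will overlap with time to UPCR ≤0.5.
4. State in SAP 6.11.4 that the responder-only summary is the exception to the ITT population.

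Cost: the responder-only p-value is lost, and the SAP needs a change entry, revised wording and one revised table. Sample size and alpha do not change.
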